We will provide data from the 20 sites and Find and Treat to the Health & Social Care Information Centre (HSCIC). These records will be list cleaned and then linked by HSCIC to the Hospital Episode Statistics (HES) database to provide data on hospitalisations and A&E attendances and deaths for individuals in the 20 sites and Find and Treat database. In order to be able to identify co-morbidities more accurately we will request data on all previous admissions for these groups for identification of

comorbidities but analyses of admission rates will be confined to the period November 2008 – November 2016.

Study design:

We will construct a virtual cohort that will take first date of admission as the entry point (earliest November 2008) or, for control groups an admission matched by month and year restricted to individuals over the age of 18. Exit from the virtual cohort will be at the end of November 2016 or, if earlier, date of death. We will conduct person-level analyses using Poisson regression to compare overall hospitalisation rates, emergency admission rates, all cause mortality and avoidable mortality rates in:

- 1) Homeless people using the different categories of SIHCC service (clinically led services - sites 1&2, 7-13; non-clinically led services - sites 3&4, 14-20)
- 2) Find and Treat Homeless population and sites 5&6 with standard usual care
- 3) Socially deprived non-homeless population.

We will also conduct analyses at the level of the hospital admission whereby through knowledge of the dates of SIHCC involvement and service user group we will be able to classify hospital admissions in the period November 2008- November 2016) into the following groups:

- 1) Admissions in a socially deprived non homeless population
- 2) Admissions in the general homeless population (Find and Treat data)
- 3) Admissions in homeless service users prior to their first engagement with SIHCC
- 4) Admissions in homeless service users where there is evidence of SIHCC support for that admission
- 5) Admissions in homeless service users that occur following SIHCC support but where there is no record of support for the subsequent admission.

We will use Cox regression survival models and Kaplan Meir plots (accounting for clustering at the level of the hospital and individual) to explore how admissions in these groups compare in terms of the following primary outcomes:

- 1) Time from discharge to next A&E attendance

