- 2) 28 day emergency readmission rates (these are a commonly used indicator within the NHS)
- 3) Time from discharge to next hospital inpatient readmission

Secondary outcomes we will examine include:

- 1) Time from admission to death
- 2) Duration of inpatient admission
- 3) Time from admission to mortality from causes amenable to healthcare
- 4) Time from discharge to admission with ambulatory care sensitive (ACS) conditions
- 5) Time from discharge to next planned admission,
- 6) Overall readmission rates
- 7) Unscheduled readmission rates
- 8) All cause mortality
- 9) International Classification of Diseases 10th Revision chapter-specific mortality
- 10) In-patient costs using Health Resource Group

For those service users with quality of life data we will explore how this changes following involvement of services and how it compares to the measures of quality of life derived from studies within Find and Treat service users and within socially deprived non-homeless groups.

A variety of mortality groupings have been developed to identify causes of death that could be considered avoidable through better medical care depending on age at which they occur. The proposals for the Public Health Outcome Monitoring framework take a similar approach and focus on key areas of avoidable mortality namely: mortality from suicide, communicable diseases, excess

seasonal mortality and, in persons aged less than 75 years, cardiovascular disease, cancer, chronic liver disease and chronic respiratory diseases. All of these are useful indicators within homeless populations.

Sample size:

Our sample size is based upon our estimates of historical data from the two types of SIHHC services (non-clinically led SIHHC services vs. clinically led SIHHC). We estimate that each type will have data from approximately 2,208 individuals for the two-year duration of the study, based on the services seeing on average 92 people per month.

From previous health service evaluation data on homeless groups we expect hospitalisation rates to be 0.7 episodes per person-year for homeless individuals admitted to hospital. An important reduction in readmission rates would be 10%. To undertake a sample size calculation to determine the study size required to detect such a reduction in readmission rates, the following variables were defined:

μ_0 = mean readmission rate in the baseline group = 0.7 episodes per person-year

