μ_1 = mean readmission rate in the SIHHC group = 0.6 episodes per person-year

$v=1.96$ =percentage point of the normal distribution corresponding to a 5% two-sided significance level

$u=0.84$ =one-sided percentage point of the normal distribution corresponding to (100%- type II error [FN / (TP + FN)]) at 80% power

Using the following equation we estimated minimum sample size (per group) required for comparison of two rates (readmissions per person-year):

$$\begin{aligned} & (u+v)^2 * (\mu_1 + \mu_0) / (\mu_1 - \mu_0)^2 \\ & (0.84+1.96)^2 *(0.7 + 0.6) / (0.7 - 0.6)^2 \\ & =1019 \text{ person-years per group} \end{aligned}$$

Adjustment for confounders as far as is possible within the analysis results in a doubling of sample size (additional 10% per confounder; likely 10 confounding variables). Therefore 2038 person-years are required per group. Assuming that the SIHHC clinically led and non-clinically led sites see on average 90 service users each month during the study period (which for the purposes of this calculation we have assumed this to be November 2013-November 2015 as many services may have been shut down before this time period and in some we may collect data at an earlier point) we estimate that this translates to a total 2,160 individuals at each of these two types of service.

Follow up: For the primary analysis, individuals will enter the cohort on date of first hospital admission (earliest November 2008) and will be censored at the end of the study period (November 2016) or death, whichever ever comes first.

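### Admission-level mortality outcomes let one death count in several groups, which biases supported v pre-engagement admissions strongly and dilutes supported v later unsupported admissions

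*Protocol*

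**What the plan says.** All references are to the protocol, Stage 3b, Comparative Effectiveness Analysis.

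- **Unit (Study design).** "We will also conduct analyses at the level of the hospital admission".
- **Groups (Study design).** Three of the five groups come from the same people. Group 3: "Admissions in homeless service users prior to their first engagement with SIHCC". Group 4: "Admissions in homeless service users where there is evidence of SIHCC support for that admission". Group 5: "Admissions in homeless service users that occur following SIHCC support but where there is no record of support for the subsequent admission". Groups 1 and 2 are other populations.
- **Model (Study design).** "We will use Cox regression survival models and Kaplan Meir plots (accounting for clustering at the level of the hospital and individual) to explore" how the groups compare. This sentence leads into the three primary outcomes; the list of secondary outcomes follows.
- **Outcomes concerned.** Secondary outcome 1, "Time from admission to death", and secondary outcome 3, "Time from admission to mortality from causes amenable to healthcare".
- **End of follow-up.** Study design has people leave the cohort at the end of November 2016 or at death. The Follow up paragraph, after the sample size calculation, says that individuals "will be censored at the end of the study period (November 2016) or death, whichever ever comes first". No separate rule is given for admission-level records.
- **A further mortality analysis.** Study design also plans a person-level Poisson analysis of all-cause and avoidable mortality.

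**The concern.** When the clock starts at every admission and stops only at death or November 2016, the records of one person overlap. A person admitted before engagement, then with support, then without support, who later dies, supplies an event to groups 3, 4 and 5. The clocks of the first two records keep running through time that belongs to the later groups. A clustered standard error allows for the correlation between these records but does not change the group to which the death and the time are assigned.

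Group 3 has an additional fault. An admission can be labelled pre-engagement only if the person lived long enough to engage later. The time up to engagement is therefore free of death by definition (immortal time).

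At stake are the survival comparisons of supported with unsupported admissions. One could suggest that support harms, and the other could understate a benefit.

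**Working it through.** **Plan's own figure.** The protocol gives no event count, effect size or power for mortality. Its one calculation for this comparison concerns readmission rates, and it reproduces: (0.84 + 1.96)² × (0.7 + 0.6) / (0.7 − 0.6)² = 7.84 × 1.3 / 0.01 = 1019.2 person-years per group, doubled to 2038.4. It does not bear on deaths.

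**Step 1: structure, with no assumed values.** Take admissions at times t3 < t4 < t5 in groups 3, 4 and 5, and death at D.

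| | Group 3 | Group 4 | Group 5 | Deaths counted |
|---|---|---|---|---|
| Run to death | D − t3 | D − t4 | D − t5 | 3 |
| Stop at next admission | t4 − t3 | t5 − t4 | D − t5 | 1 |

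Under the first rule the intervals overlap and one person is three deaths. Under the second, time adds up to D − t3 and the death falls in group 5. Group 3 then has no deaths at all, because every group 3 admission is followed by a later, supported one.

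**Step 2: how much overlap to expect.** The protocol gives 0.7 admissions per person-year and a window from November 2008 to November 2016: 0.7 × 8 = 5.6 further admissions for someone who enters at the start. Service data generally begin in November 2013. A November 2008 admission in group 3 therefore carries about 5 of its possible 8 years with death excluded.

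**Step 3: simulation.** From the protocol: 0.7 admissions per year, the 8-year window, support possible in the last 3 years, and only people with at least one supported admission kept. Assumed, because the protocol gives no values: constant hazards, 3% or 6% deaths per year, and support recorded for 40% to 80% of admissions in those last 3 years. The true effect is either none or a ratio of 0.7 acting until the next admission.

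| Quantity | Run to death | Stop at next admission |
|---|---|---|
| Records per death | 3.5 to 4.0 | 1 |
| Deaths in more than one of groups 3 to 5 | 70% to 84% | none |
| Group 4 v 3, no true effect | rate ratio about 2.6; Cox hazard ratio about 4.7 to 5.2 | cannot be estimated (no group 3 deaths) |
| Group 4 v 5, no true effect | 1.00 to 1.05 | 1.01 to 1.06 |
| Group 4 v 5, true 0.7 | 0.76 to 0.83 | 0.66 to 0.75 |

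The two figures for group 4 v 3 measure one bias in two ways. The rate ratio averages over all follow-up. The Cox model compares records at equal time since admission, so it gives more weight to early follow-up, where group 3 is largely protected.

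For group 4 v 5, a true reduction of 1 − 0.70 = 30% appears as 1 − 0.83 = 17% to 1 − 0.76 = 24%. At twice the admission rate (1.4 per year) each death closes 5.7 to 6.5 records.

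**The case against.** The strongest reply is that the protocol never says admission records run past the next admission. Both exit statements concern individuals, and a censoring rule for secondary outcomes could properly be left to a statistical analysis plan. That stands in part: the rule is inferred. It is, however, the only rule in the document, and an outcome defined as time from admission to death ends at death when read plainly. A stop at the next admission would not rescue group 3 either, since that group would then have no deaths. The fault in that contrast comes from how the group is defined.

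Other points stand and limit the concern:

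- The sentence on Cox models introduces the primary outcomes. These end at the next attendance or readmission, or at 28 days, so multiple counting of deaths does not reach them.
- The person-level Poisson analysis counts each death once. It compares types of service and populations, not supported with unsupported admissions, so it does not replace the affected contrasts.
- Survival from an index admission, whatever care follows, is a legitimate but different question. If the effect of support persists beyond the next admission, group 5 is itself exposed, and group 4 v 5 is near 1 with or without a stop.
- With no true effect, group 4 v 5 shows almost no false difference.

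A reader might also extend the point to time to a planned admission or to an ambulatory care sensitive admission. The documents do not support that: stopping at any intervening admission would redefine those outcomes, and no bias has been computed for them.

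**Conclusion.** The concern holds for secondary outcomes 1 and 3, compared at admission level across groups 3, 4 and 5, if the stated exits apply to admission records. There are two biases, and they differ in kind.

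- **Group 4 v 3:** biased away from no difference and strongly against supported admissions (rate ratio about 2.6, hazard ratio about 4.7 to 5.2, with no true effect). No censoring rule repairs it.
- **Group 4 v 5:** a benefit that lasts until the next admission is diluted, from 0.7 to about 0.76 to 0.83.

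The sharing of deaths, and the absence of group 3 deaths under a stop rule, follow from the definitions alone. The sizes depend on the assumed death rates, support probabilities and constant hazards.

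A reader might infer that all mortality results are diluted, or that the published deaths per group must exceed the people who died. Neither follows: dilution describes only group 4 v 5, the Poisson analysis is separate, and the protocol fixes no format for reporting deaths.

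**What to change.** 1. State that group 3 is not a comparator for mortality.
2. For the group 4 v 5 mortality contrast, use start-stop records with SIHHC support as a time-varying exposure. Each admission contributes time until the earliest of death, the next admission or the end of November 2016. Each death is then counted once, in the group of the most recent admission.
3. Keep the allowance for clustering by hospital and individual, and report deaths as numbers of people.
4. Leave the primary outcomes, the person-level Poisson analysis, and the planned-admission and ambulatory care sensitive outcomes as they are.

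The cost is wording and programming. Admission, discharge and death dates are already among the fields in Appendix One, Box 5, and Study design already relies on the dates of SIHHC involvement. The downside is that the estimate then describes the period up to the next admission, not all later survival, and the report should say so.

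### With death censored, the Kaplan-Meier plots for time to next A&E attendance and time to next readmission overstate the proportion of admissions followed by that event

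*Protocol*

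**What the plan says.** Under Comparative Effectiveness Analysis, Study design, the protocol sorts hospital admissions into five groups: deprived non-homeless, general homeless, and homeless service users before, with and after SIHHC support. It then gives the method: "We will use Cox regression survival models and Kaplan Meir plots (accounting for clustering at the level of the hospital and individual". The sentence continues "to explore how admissions in these groups compare in terms of the following primary outcomes".

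Three primary outcomes follow. The first is "Time from discharge to next A&E attendance". The second is "28 day emergency readmission rates (these are a commonly used indicator within the NHS". The third is the time from discharge to the next inpatient readmission. The first and third have no fixed horizon.

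Death is handled in two places. The Study design text says "Exit from the virtual cohort will be at the end of November 2016 or, if earlier, date of death". The Follow up paragraph, after the sample size calculation, says individuals "will be censored at the end of the study period (November 2016) or death, whichever ever comes first". Both rules are written for persons in the cohort. No separate rule is given for the admission-level models, so those models naturally inherit this one. Death is not described as a competing event, and no cumulative incidence estimator is named.

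**The concern.** Kaplan-Meier treats a censored subject as still able to have the event later. That suits someone still alive when the study ends in November 2016. It does not suit someone who has died, for whom readmission or A&E attendance is no longer possible. With death censored, 1 minus Kaplan-Meier describes a hypothetical setting in which nobody dies, not the proportion of admissions that are followed by a return to hospital.

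The gap grows with follow-up and with mortality. The plots set homeless groups beside a deprived non-homeless group, and mortality is itself among the secondary outcomes. If death rates differ between groups, the curves can hide a difference in the proportion actually readmitted. That absolute proportion is what a commissioner would be likely to take from such a plot.

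**Working it through.** **Inputs from the protocol (Sample size).** Readmission rates of 0.7 (baseline) and 0.6 (SIHHC) per person-year; normal deviates 1.96 and 0.84.

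**The plan's own figure first.** (0.84 + 1.96)² × (0.7 + 0.6) / (0.7 − 0.6)² = 7.84 × 1.3 / 0.01 = 1,019.2. This reproduces the stated 1,019 person-years per group, doubled to 2,038 for confounders. It compares rates per person-year and does not depend on the plots.

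**Assumed inputs.** The protocol gives no death rate, so m = 0.02, 0.05 and 0.08 per person-year are used. Hazards are taken as constant, and 0.7 per person-year is used as the hazard λ of the next readmission after discharge. No A&E attendance rate is given, so the figures are for readmission; the same formulas apply to A&E attendance.

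**Formulas.**
- 1 minus Kaplan-Meier, death censored: 1 − exp(−λt)
- Proportion actually readmitted (cumulative incidence): λ/(λ+m) × [1 − exp(−(λ+m)t)]

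**Worked case, m = 0.05, t = 3 years.** Kaplan-Meier: 1 − exp(−2.1) = 87.75%. Cumulative incidence: 0.7/0.75 × [1 − exp(−2.25)] = 83.50%. The overstatement is 4.3 points.

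**Results at λ = 0.7** (differences taken before rounding):

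| Time | 1 − Kaplan-Meier | Actual, m = 0.02 | Actual, m = 0.05 | Actual, m = 0.08 | Overstatement, points |
|---|---|---|---|---|---|
| 1 year | 50.34% | 49.90% | 49.25% | 48.60% | 0.4 / 1.1 / 1.7 |
| 3 years | 87.75% | 86.01% | 83.50% | 81.10% | 1.7 / 4.3 / 6.7 |
| 8 years | 99.63% | 96.92% | 93.10% | 89.57% | 2.7 / 6.5 / 10.1 |

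A simulation of 400,000 admissions at λ = 0.7, m = 0.05 gave 49.3%, 83.6% and 93.1% at 1, 3 and 8 years, agreeing with the formula.

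**Scale.** The contrast used for sample size, 0.7 against 0.6, is 87.75% − 83.47% = 4.3 points on the Kaplan-Meier scale at 3 years. Two groups both at λ = 0.7, with death rates 0.02 and 0.08, have identical Kaplan-Meier curves, yet 86.0% and 81.1% are actually readmitted by 3 years. That is a hidden gap of 4.9 points.

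**28-day outcome.** At λ = 0.7, 1 − Kaplan-Meier is 5.2% and the overstatement is about 0.02 points or less for m up to 0.08. Even with 28-day readmission of 20% and a death rate of 0.30 per person-year (both assumed), it is about 0.2 points.

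**The case against.** The strongest reply is that no planned estimate or test is wrong. The plots accompany Cox models in an exploratory comparison, and the protocol never says that a multi-year proportion will be read from them. Cox regression with death censored validly estimates the cause-specific hazard ratio, and Poisson rates per person-year alive are not inflated. The one fixed-horizon primary outcome is 28-day readmission, where the error is negligible. The choice of graph might also be left to a statistical analysis plan, which is not at hand.

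Much of this stands and limits the point to the plots and proportions taken from them. It does not remove the point: the protocol itself names the estimator and gives the only rule for death, and together they yield the wrong quantity for two primary outcomes.

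Four stronger readings are tempting but unsupported:

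- A reader might infer that cause-specific death will also be shown by Kaplan-Meier, since "Time from admission to mortality from causes amenable to healthcare" is a listed outcome. It is secondary, and the sentence naming the plots covers primary outcomes only. Person-level avoidable mortality rates are assigned to Poisson regression. The secondary times to planned and ambulatory-care-sensitive admission are likewise outside that sentence.
- A reader might infer that the error is always larger in the group with higher mortality. That holds at equal readmission hazards. With assumed figures at 8 years, hazard 0.7 and death rate 0.05 give 6.5 points, while hazard 0.2 and the lower death rate 0.04 give 8.7.
- A reader might express the error in standard errors using the 2,160 people per service type. That would treat them as independent and fully followed to 3 years. Recruitment is assumed over November 2013 to November 2015 with censoring in November 2016, so follow-up on that basis is about 1 to 3 years, and admissions are clustered by hospital and person.
- A reader might apply 8 years throughout. Scheme data mostly start in November 2013, so 3 years is about the limit for supported admissions. Longer horizons concern comparators and earlier admissions.

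**Conclusion.** The point holds for the Kaplan-Meier plots of time to next A&E attendance and time to next inpatient readmission, and for any proportion read from them. For readmission the overstatement is modest at 1 year, and by 3 years it can match the contrast on which the study is sized. These sizes rest on assumed mortality, constant hazards, and carrying the person-level censoring rule into the admission-level models. The direction does not depend on the mortality figure chosen: wherever deaths occur before the event, 1 minus Kaplan-Meier is too high. The 28-day outcome, the Cox cause-specific hazard ratios, the Poisson rates and the sample size stand. The change should be made, but it corrects the presentation of absolute risk and does not call the planned regression comparisons into question.

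**What to change.** In Study design, replace the Kaplan-Meier plots for the two open-ended primary outcomes with Aalen-Johansen cumulative incidence curves, taking death as the competing event, and plot the cumulative incidence of death beside them. Keep the Cox models and label their results as cause-specific hazard ratios. State explicitly that this handling of death applies to the admission-level analyses. Do the same for secondary time-to-admission or cause-specific death outcomes only if they are to be plotted in the same way, with death, or death from other causes, as the competing event.

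The cost is a sentence or two of wording and a standard software option. Date and cause of death are already among the linked variables requested in Appendix One, Box 5, so no new data are needed and the sample size does not change.

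### The sample size names a 10% reduction in readmission rate as important but is computed for 0.7 v 0.6 per person-year, a 14.3% reduction

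*Protocol*

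**What the plan says.** The Sample size section under Comparative Effectiveness Analysis expects 0.7 hospital episodes per person-year. It then says "An important reduction in readmission rates would be 10"% and describes the calculation as one to "determine the study size required to detect such a reduction in readmission rates".

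The inputs that follow are "mean readmission rate in the baseline group = 0.7 episodes per person-year" and "mean readmission rate in the SIHHC group = 0.6 episodes per person-year", with a two-sided 5% level and 80% power. The result is 1,019 person-years per group. The protocol doubles it for adjustment, at 10% for each of about ten confounders, and concludes: "Therefore 2038 person-years are required per group".

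The next sentence sets this beside an expected 2,160 individuals at each of the two types of service (90 a month). Earlier in the section the figure is 2,208 (92 a month). The Follow up paragraph starts follow-up at first hospital admission, November 2008 at the earliest, and ends it in November 2016 or at death. Mean follow-up per person is not given.

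**The concern.** The effect called important and the effect entered in the formula differ, and no sentence explains the change. The text ties the two together by saying that the calculation is for that same reduction. Because the required size varies roughly with the inverse square of the difference, moving from 0.07 to 0.10 episodes per person-year about halves it.

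As written, the section tells the reader that 2,038 person-years per group give 80% power for a 10% reduction. They do not. Anyone using the section to judge how informative a non-significant comparison is would be working from the wrong effect size.

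**Working it through.** **Inputs, all from the Sample size section:** baseline rate 0.7; SIHHC rate 0.6 as entered; u = 0.84 (80% power); v = 1.96 (two-sided 5%); factor 2 for confounders; 90 individuals a month for 24 months = 2,160 per type.

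**1. Reproduce the stated figure.** The protocol's formula is (u + v)² × (μ1 + μ0) / (μ1 − μ0)².
- (0.84 + 1.96)² = 7.84
- 7.84 × 1.3 / 0.1² = 1,019
- 1,019 × 2 = 2,038

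Both figures reproduce.

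**2. Effect actually entered.** 0.1 / 0.7 = 14.3%. A 10% reduction is 0.7 × 0.9 = 0.63, a difference of 0.07.

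**3. Same formula with the stated effect.**
- 7.84 × 1.33 / 0.07² = 2,128 person-years per group
- 2,128 × 2 = 4,256 after doubling
- 2,128 / 1,019 = 2.09 times the stated size

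**4. Power for 10% at the stated requirement.** Invert the formula and carry the doubling as a variance factor of 2:

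power = Φ(0.07 / √(2 × 1.33 / PY) − 1.96)

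At PY = 2,038: 0.07 / 0.0361 = 1.938, and Φ(1.938 − 1.96) = 49%. A version on the log rate ratio also gives 49%.

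**5. Power for 10% at the expected number of individuals.** Mean follow-up is an assumption here, shown as a range (2,160 per type, doubling kept):

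| Mean follow-up | Person-years per type | Power for 10% |
|---|---|---|
| 1 year | 2,160 | 51% |
| 1.5 years | 3,240 | 69% |
| 2 years | 4,320 | 81% |

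With 2,208 individuals at one year each, power is 52%. Two years is the mean if people enter evenly from November 2013 to November 2015 and are followed to November 2016 (range one to three years). That exceeds 4,256 by 64 person-years, or 1.5%. The mean follow-up needed to reach 4,256 is 4,256 / 2,160 = 1.97 years.

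**The case against.** **The 10% may mean 0.1 episodes per person-year.** On that reading the arithmetic is consistent and only the percentage is wrong. The text does not say so, and a rate per person-year is not a percentage. The wording would still need correcting, and this is one of the two remedies below.

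**A reader might infer that the study as planned has only 49% power for a 10% reduction.** The protocol does not support that. The 2,038 person-years are its stated requirement, not its expected yield. Anyone who enters by November 2015 and survives contributes at least a year, and the two-year scenario restores about 81%. Cohort entry can go back to November 2008, which would add further person-time. However, the admission-level analysis separates admissions before first SIHHC engagement from supported ones, so that time is not clearly follow-up under the service.

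**A reader might infer that setting 2,160 individuals against 2,038 person-years inflates the power.** It is loose, but it amounts to assuming one year each. That is near the floor under the stated follow-up rule, so it probably understates the information available.

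**A reader might infer that the calculation sizes only a secondary outcome.** The rate does match "Overall readmission rates" in the secondary list. It also matches the planned Poisson comparison of hospitalisation rates, and it concerns the same event as the third primary outcome, time to next inpatient readmission. Power for the primary outcomes may be given in an analysis plan that is not shown.

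**The doubling might be treated as a margin.** Without it, 2,038 person-years give 78% power for 10%. But the protocol presents the doubling as the cost of confounder adjustment, so it cannot also serve as spare capacity.

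**Conclusion.** The inconsistency is certain: 10% is stated and 14.3% is computed. For 10%, the protocol's own formula needs 2,128 person-years per group, or 4,256 after doubling, about 2.09 times the stated figures. The 80% power claimed for 10% at 2,038 person-years is really about 49%.

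Whether the study itself falls short for 10% cannot be settled from the protocol. With the doubling and 2,160 individuals per type, power runs from about 51% to 81% as mean follow-up goes from one to two years. All of these figures take the protocol's Poisson formula and inflation factor as given. They are before deaths, records that cannot be linked, overdispersion and clustering, for which the sample size section gives no figure. The two-year case has little room for any of them.

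**What to change.** Make the effect and the calculation agree, in one of two ways:
- state that the study is sized for a reduction of 0.1 episodes per person-year (14%), and keep 1,019 and 2,038; or
- keep 10%, set the SIHHC rate to 0.63, and state 2,128 person-years per group, 4,256 after doubling.

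In either case, replace the comparison with a number of individuals by one with expected person-years per type (individuals × mean follow-up × linkage rate), and state the mean follow-up and linkage rate assumed.

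The cost is a few sentences in the Sample size section. No extra recruitment is needed, since numbers depend on how many people the services see. The price is a less favourable statement: either a larger detectable effect or a larger requirement.
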